5.2 Exclusion criteria

Subjects meeting any of the following criteria are not eligible for inclusion in this study.

1. Secondary causes of MN, e.g. systemic autoimmune diseases, solid or hematological malignancies, infections or chronic intake of drugs (e.g. gold salts, NSAIDs, penicillamines)
2. Diagnostic renal biopsy showing evidence of crescent formation in glomeruli, suggestive of an alternative or additional diagnosis to primary idiopathic MN.
3. Previous treatment with B-cell depleting or B-cell modifying agents such as, but not limited to rituximab, belimumab, daratumumab or bortezomib.
4. Previous treatment with immunosuppressive agents such as cyclophosphamide, chlorambucil, mycophenolate mofetil (or equivalent), cyclosporine, tacrolimus or azathioprine within 90 days prior to Day 1. Low dose systemic corticosteroid therapy is permitted, though the subject should have been on stable dose equivalent to ≤ 10 mg prednisolone for at least 90 days prior to Day 1

5. Commercially Confidential Information

6.

Commercially Confidential Information

7.

8.

9.

10. Presence or suspicion (based on judgment of the investigator) of any active infection within 30 days prior to Day 1, or history of severe recurrent bacterial infections
11. Pregnancy or nursing (lactation), where pregnancy is defined as the state of a female after conception and until the termination of gestation, confirmed by a positive human Chorionic Gonadotropin (hCG) laboratory test
12. Women of child-bearing potential, defined as all women physiologically capable of becoming pregnant, unless they are using effective contraception during dosing and for 1 week after stopping of LNP023 or for 12 months after stopping rituximab. *Effective contraception methods include:*
 - Barrier methods of contraception: Condom or Occlusive cap.
 - Use of oral, injected or implanted hormonal methods of contraception, or other forms of hormonal contraception that have comparable efficacy (failure rate <1%), for example hormone vaginal ring or transdermal hormone contraception, or placement of an intrauterine device (IUD) or intrauterine system (IUS). In case of use of oral contraception, you should have been stable on the same pill for a minimum of 3 months before taking the study treatment.
 - Total abstinence (When this is in line with your preferred and usual lifestyle. Periodic abstinence and withdrawal are not acceptable methods of contraception)
 - Female sterilization (surgical bilateral oophorectomy [with or without hysterectomy], total hysterectomy or tubal ligation, at least six weeks before taking study treatment. In case of oophorectomy alone, only when your reproductive status has been confirmed by follow up hormone level assessment)
 - Your sole partner is a vasectomized male who was sterilized at least 6 months prior to screening.

In case of use of oral contraception, women should be stable on the same pill for a minimum of 3 months before taking study treatment.

If local regulations deviate from the contraception methods listed above and require more extensive measures to prevent pregnancy, local regulations apply and will be described in the ICF.

Women are considered post-menopausal and not of child-bearing potential if they have had 12 months of natural (spontaneous) amenorrhea at screening with an appropriate clinical profile (e.g. age appropriate, history of vasomotor symptoms) or have had surgical bilateral oophorectomy (with or without hysterectomy), total hysterectomy or tubal ligation at least six weeks prior to screening. In the case of oophorectomy alone, only when the reproductive status of the woman has been confirmed by follow up hormone level assessment is she considered not of child-bearing potential

13. History of immunodeficiency diseases, including a positive HIV test result at screening visit
14. Commercially Confidential Information

15.

16.

17.

18.

Commercially Confidential Information

19.

20.

21.

22.

23. Known contraindications for the use of rituximab, including hypersensitivity to the active substance or to murine proteins, or to any of the excipients (sodium citrate, polysorbate 80, sodium chloride, sodium hydroxide, hydrochloric acid, water for injections).
Other contra-indications for the use of rituximab, including active, severe infection, patients in a severely immunocompromised state, severe heart failure (NYHA ClassIV) or severe, uncontrolled cardiac disease.

24. Evidence of TB infection (active or latent) determined by positive QuantiFERON test or positive purified protein derivative (PPD) test (≥ 5 mm induration) at screening visit or within 2 months prior to screening visit, according to national guidelines. Patients with a positive or indeterminate QFT test may participate in the study if a full tuberculosis work-up (according to local practice/guidelines) completed within 12 weeks prior to randomization, establishes conclusively that the patient has no evidence of active or latent tuberculosis. If presence of latent TB infection is established then treatment for TB as per national guidelines must have been initiated and completed prior to randomization. In the absence of national guidelines, the following has been demonstrated: TB has been treated adequately by antibiotics, cure can be demonstrated and risk factors resulting in TB exposure and contracting have been removed.
- Subjects who in the opinion of the investigator and based upon an appropriate evaluation, have a risk of reactivation of TB that precludes the use of conventional immunosuppression

6 Treatment

6.1 Study treatment

Details on the requirements for storage and management of study treatment, and instructions to be followed for subject numbering, prescribing/dispensing, and taking study treatment are outlined in the SOM.

6.1.1 Investigational and control drugs

The investigational drug LNP023 will be prepared by the sponsor as 25 mg and 100 mg capsules. Investigational drug will be supplied to the investigator as patient-specific kits.

All LNP023-treated subjects will be administered two capsules at morning and evening during treatment period. Refer to SOM for details on dispensing.

The investigational drug rituximab as concentrate for solution for infusion will be provided locally. Refer to the SOM for specific instructions on preparation.

Table 6-1 Investigational and control drug

Investigational/ Control Drug	Pharmaceutical Dosage Form	Route of Administration	Supply Type	Sponsor (global) or locally provided
LNP023 25 mg	Capsules	Oral use	patient specific kits	Sponsor (global)
LNP023 100 mg	Capsules	Oral use	patient specific kits	Sponsor (global)
Rituximab 10 mg/mL*	Concentrate for solution for infusion	Intravenous use	Open label subject packs	Locally provided

* Concentration can vary based on country availabilities.

6.1.2 Additional study treatments

No other treatment beyond investigational drugs are included in this trial.

6.1.3 Treatment arms/group

This is an open-label study. Subjects will be assigned at Day 1, or up to 4 days before, if all the inclusion and exclusion criteria are verified, to one of the following treatment arms in a ratio of 1:1

6.2 Other treatment(s)

Not applicable.

6.2.1 Concomitant therapy

The investigator must instruct the subject to notify the study site about any new medications he/she takes after being enrolled in the study.

Subjects must receive vaccinations against *N. meningitidis*, *S. pneumoniae* and *H. influenzae* at least 28 days prior to Day 1 independent of the treatment arm allocation (see [Section 8.4.4](#) for more details).

Prophylactic antibiotics may be given at investigator's discretion in accordance with local practice for patients receiving immunosuppressive or complement pathway blocking therapies. Prophylactic antibiotic therapy may be given for tuberculosis as per local guidelines.

Subjects will remain on their supportive therapy, e.g. ACEi and/or ARB and or systemic corticosteroids, with or without diuretics, statins or antihypertensive therapy(ies) for the duration of the trial. To be commenced on randomized treatment, subjects must have been on stable therapy with an ACEi and/or ARB, defined as <25% dose change over at least 8 weeks at the maximally tolerated dose ([KDIGO 2012](#)) and, if used as part of local standard of care, systemic corticosteroids at a stable dose that does not exceed the equivalent of 10 mg prednisolone daily over at least 90 days prior to Day 1.

Subjects in the rituximab arm should receive pre-medication consisting of an anti-pyretic and an antihistamine (e.g. paracetamol and diphenhydramine) before each dose as per local standards. Where a single dose of glucocorticoid (e.g. methylprednisolone or hydrocortisone) is used in addition to these measures as part of local standard of care, then this is permitted.

All medications, procedures, and significant non-drug therapies (including physical therapy and blood transfusions) administered after the subject was enrolled into the study must be recorded on the appropriate Case Report Forms.

Medication entries should be specific to trade name, the single dose and unit, the frequency and route of administration, the start and discontinuation date and the reason for therapy.

Each concomitant drug must be individually assessed against all exclusion criteria/prohibited medication. If in doubt, the investigator should contact the sponsor medical monitor before randomizing a subject or allowing a new medication to be started. If the subject is already enrolled, contact sponsor to determine if the subject should continue participation in the study.

6.2.1.1 Permitted concomitant therapy requiring caution and/or action

LNP023

Commercially Confidential Information

Rituximab

The co-administration of rituximab did not have any effect on the pharmacokinetics of fludarabine or cyclophosphamide and in addition there was no apparent effect of fludarabine and cyclophosphamide on the pharmacokinetics of rituximab. Co-administration of methotrexate had no impact on rituximab pharmacokinetics ([Rituximab SmPc 2019](#)).

6.2.2 Prohibited medication

Commercially Confidential Information

The investigator should consult with the Novartis medical expert prior to treating a patient with this type of co-medication.

Use of the treatments displayed in the tables below is NOT allowed.

Table 6-2 Prohibited medication for LNP023 arm

Medication	Prohibition period	Action taken
Live Vaccination	From 28 days prior to dosing until the end of randomized treatment period, unless immunosuppressive therapy commenced during safety follow-up period	Discontinue study treatment during treatment period. Ongoing study visits to collect outcome data.
Immunosuppressive agents such as but not limited to cyclophosphamide, MMF or mycophenolate sodium, cyclosporine, tacrolimus, sirolimus, systemic corticosteroids at a dose greater than 10mg/day prednisolone equivalent	90 Days prior to dosing until end of randomized treatment period.	Discontinuation of study treatment to be discussed and agreed on a case by case basis. Ongoing study visits to collect outcome data where study treatment is discontinued.
Biological agents such as, rituximab, infliximab, canakinumab, etc.	At any point prior to randomization or during the randomized treatment period	Discontinue study treatment during treatment period. Ongoing study visits to collect outcome data.

Commercially Confidential Information

Table 6-3 Prohibited medication for rituximab arm

Medication	Prohibition period	Action taken
Live Vaccination	From 28 days prior to dosing until the end of randomized treatment period, unless immunosuppressive therapy commenced during safety follow-up period	Discontinue study treatment during treatment period. Ongoing study visits to collect outcome data.
Immunosuppressive agents such as but not limited to cyclophosphamide, MMF or mycophenolate sodium, cyclosporine, tacrolimus, sirolimus, systemic corticosteroids at a dose greater than 10mg/day prednisolone equivalent	90 prior to dosing and until end of randomized treatment period, except in case of pre-medication for infusion.	Discontinuation of study treatment to be discussed and agreed on a case by case basis. Ongoing study visits to collect outcome data where study treatment is discontinued.
Biological agents such as infliximab, canakinumab, etc.	At any point prior to randomization. Biological agents other than rituximab study drug should not be administered during the randomized treatment period	Discontinue study treatment during treatment period. Ongoing study visits to collect outcome data.

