6.6.2 Recommended treatment of adverse events

At present, there is insufficient information to provide specific recommendations regarding treatment of AEs for LNP023 arm. There is no treatment that can reverse the activity of LNP023. LNP023 is a small molecule CCI. Potential AEs should therefore be treated symptomatically at the discretion of the investigator. Medication used to treat AEs must be recorded on the concomitant medications/significant non-drug therapies CRF.

Rituximab-related AEs should be treated in accordance with local guidelines. Patients who develop infusion reactions should be monitored closely. The rituximab infusion should be discontinued and medical treatment with corticosteroids, antihistamine and paracetamol should be administered in accordance with local guidelines for severe reactions. Rituximab therapy should be discontinued in the event of severe mucocutaneous reactions, hepatitis B reactivation, neurological complications or other serious adverse events deemed by the investigator to be treatment related.

Where response to treatment is deemed inadequate the investigator may, at their discretion, withdraw the subject from the study and commence local standard of care. Subjects should continue with the scheduled study visits to allow collection of outcome and adverse event data.

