9.1 Discontinuation

9.1.1 Discontinuation of study treatment

Discontinuation of study treatments for a patient occurs when study treatment is stopped earlier than the protocol planned duration. Discontinuation of study treatment can be decided by either the patient or the investigator. If discontinuation of study treatment occurs, the investigator must determine the primary reason for the patient's premature discontinuation of study treatment and record this information on the Dosage Administration CRF.

Patients who discontinue study treatment or who decide they do not wish to participate in the study further should NOT be considered withdrawn from the study UNLESS they withdraw their consent. Where possible, they should perform the assessments as per assessment schedule. If they fail to return for these assessments for unknown reasons, every effort (e.g. telephone, e-mail, letter) should be made to contact the patient/pre-designated contact as specified. This contact should preferably be done according to the study visit schedule.

Test treatment (LNP023) or reference treatment (rituximab) must be discontinued under the following circumstances:

- Patient decision - Patients may choose to discontinue study treatment for any reason at any time.
- The investigator believes that continuation would negatively impact the safety of the patient or the risk/benefit ratio of trial participation.
- Any protocol deviation that results in a significant risk to the patient's safety.
- Pregnancy
- Infections that are considered, by the investigator, not possible to effectively manage whilst the patient is receiving LNP023 or rituximab.
- Use of prohibited treatment as outlined in [Table 6-2](#) and [Table 6-3](#) listing prohibited medications
- Any laboratory abnormalities that in the judgment of the investigator, taking into consideration the patient's overall status, prevents the patient from continuing participation in the study.
- Please see [Section 16.1 Appendix 1](#) for additional information on discontinuing treatment based on laboratory evidence of liver injury.

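### Read literally, Protocol 9.1.1 requires discontinuation for any prohibited medication, while the corticosteroid row of Tables 6-2 and 6-3 leaves it case by case; the steroid that 6.6.2 directs for a severe rituximab reaction can trigger this (minor)

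*Protocol*

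**What the plan says.** **The ban.** Protocol 6.2.2, Table 6-3 (rituximab arm), prohibits immunosuppressants, including systemic corticosteroids above 10 mg/day prednisolone equivalent, "until end of randomized treatment period, except in case of pre-medication for infusion". Table 6-2 has the same row for LNP023, with the period "90 Days prior to dosing until end of randomized treatment period" and no exemption.

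**The action in the tables.** For this row both tables say: "Discontinuation of study treatment to be discussed and agreed on a case by case basis". The rows for live vaccines and biological agents instead instruct the site to discontinue.

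**The action in 9.1.1.** Either study treatment "must be discontinued under the following circumstances". One of the listed circumstances is "Use of prohibited treatment as outlined in" Tables 6-2 and 6-3. The bullet does not separate the rows.

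**The directed care.** Section 6.6.2 says that the rituximab infusion should be stopped and that "medical treatment with corticosteroids, antihistamine and paracetamol should be administered in accordance with local guidelines for severe reactions". It gives no dose. It then lists separately what ends rituximab therapy: severe mucocutaneous reactions, hepatitis B reactivation, neurological complications, or "other serious adverse events deemed by the investigator to be treatment related".

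**Other permissions.** Protocol Sections 3, 6.2.1, 6.6 and 6.7 allow corticosteroids around the infusion only as pre-medication or prevention. For doubtful co-medication, 6.2.1 says: "If the subject is already enrolled, contact sponsor to determine if the subject should continue participation in the study".

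**The concern.** Two visible provisions cover the same event and, on their literal words, prescribe different actions. One is mandatory and the other discretionary. This affects the corticosteroid and immunosuppressant row in both arms.

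The rituximab arm has an extra trigger, because the protocol itself directs the treatment that can breach the ban. Protocol 4.5.3 says that most infusion reactions come with the first infusion, when the Day 15 dose is still to be given. A site that follows 6.6.2 and then applies 9.1.1 literally would withhold that dose. A site that follows the table row might give it. The choice decides whether the subject receives the full comparator regimen and whether the subject contributes to the primary analysis.

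**Working it through.** No sample size, power or error rate in the plan is disputed, so there is no stated figure to reproduce. The check compares the texts and then works out the consequence.

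**1. Is treatment of a reaction exempt?** The Table 6-3 exemption names pre-medication only, and so do the other permissions. Treating a reaction is neither pre-medication nor prevention. A breach arises only if the dose exceeds 10 mg/day prednisolone equivalent. The protocol gives no dose and defers to local guidelines.

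**2. Does 6.6.2 end rituximab anyway?** Not for every severe reaction. It stops the current infusion, but ends therapy only for the listed events. A severe reaction that is not serious, and is not one of those events, leaves the Day 15 dose available. A treatment-related SAE ends rituximab regardless. After a Day 15 reaction no further dose remains.

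**3. What follows if Day 15 is cancelled?** Under SAP 6.1, a single-infusion subject counts as under treatment for 3 months after that infusion.
- Day 1 + 3 calendar months = Day 90 to 93, depending on the start date.
- The earliest Day 113 visit is 113 − 3 = Day 110, and its 24h collection starts on Day 109.
- The gap is at least 109 − 93 = 16 days, so no post-baseline 24h UPCR is on treatment.
- SAP 6.1.3.3 uses data up to discontinuation and requires at least one post-baseline value, so the subject drops out of the primary model. SAP 6.2.2 scores the subject a non-responder.
- With both infusions, Day 15 + 6 months = Day 196 to 199. This is later than the last possible Day 169 visit (169 + 3 = Day 172), so both collections count.

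**4. How many subjects?** The documents give no rate of severe reactions. Protocol 4.5 says that reactions were avoided in a cited trial with 37 rituximab-treated patients, using routine premedication that included a corticosteroid.
- Assumption: read this as 0 of 37. The one-sided 95% upper limit is 1 − 0.05^(1/37) = 7.8%.
- Applied to 24 subjects: 24 × 0.078 = 1.9, so a range of 0 to 1.9 for any reaction. The exposed subset is smaller.
- Corticosteroid pre-medication is optional here, so the rate could be higher. In the 20-patient pilot in 4.2, on a different regimen, adverse effects were mainly infusion reactions and none were serious.

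**5. Effect per exposed subject on the rituximab remission rate.** At the 35.1% remission quoted in 4.3, the average loss is 35.1/24 = 1.5 points. At most it is 100/24 = 4.2 points.

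**6. Against the planned allowance.** Protocol 12.8.1 assumes 17% drop-out (9/52 = 17.3%). From 48 subjects on the two main arms to 40 evaluable, the allowance is 8/48 = 16.7%, or about 4 per arm on an equal split. This exceeds the 1.9 bound.

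**The case against.** The best counter-argument is that the texts can be reconciled. The 9.1.1 bullet refers to the tables, and the tables have an action column that deliberately distinguishes rows. Reading the bullet together with that column gives effect to every sentence, whereas the literal reading empties the case-by-case wording of meaning. Section 6.6.2 points the same way, because a severe infusion reaction alone is not on its list of events that end therapy. This is the more sensible reading. A reader might infer that the two rules are irreconcilable, and the documents do not support that. What remains is that the mandatory lead-in in 9.1.1 contains no such qualification. The sponsor-contact route in 6.2.1 does not settle which rule governs. Section 14.1 permits immediate safety treatment but leaves the discontinuation rule in force.

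The exposed case may be narrower still. The SAE definition in 10.1.2 includes medically significant events and gives intensive emergency treatment of allergic bronchospasm as an example. Many reactions that need a stopped infusion and corticosteroids could therefore be classed as serious, and related ones would end rituximab anyway. This stands, and it limits the size of the problem.

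Parts of 6.2.2 are blacked out, and administration details are left to a site manual that is not available here. An exemption could sit there. The visible Table 6-3 row is complete and 9.1.1 is visible, but certainty is not justified.

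Finally, an unlimited exemption for treating reactions would take a prolonged high-dose steroid course, in the comparator arm of an open-label proteinuria trial, out of review. This stands, and the exemption should be limited in duration.

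**Conclusion.** The point holds as a minor fault in an operative rule. As written, 9.1.1 can require discontinuation where the table would leave it to judgement, in both arms. In the rituximab arm, care that 6.6.2 directs can be the trigger. The consequence needs a severe but non-serious Day 1 reaction, a corticosteroid dose above 10 mg/day, and a site or sponsor that applies 9.1.1 literally.

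A reader might infer a biased or underpowered primary comparison. The documents do not support that. Under the 0-of-37 assumption at most about 2 of 24 subjects would have any reaction, fewer would be exposed, and the drop-out allowance is about 4 per arm. The sensitivity analysis in SAP 6.1.3.4 uses all collected data whether or not treatment stopped. If reactions are more frequent without routine corticosteroid pre-medication, the count could be higher, but the documents give no rate for that.

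The conclusion rests on the visible text and assumes that nothing blacked out in 6.2.2 already exempts treatment of a reaction.

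**What to change.** Make two wording changes at the next amendment.

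1. **Protocol 9.1.1.** Replace the bullet with: *Use of prohibited treatment, where the action stated in the relevant row of Table 6-2 or Table 6-3 is to discontinue, or where discontinuation is agreed case by case.* This resolves the mismatch for both arms.
2. **Table 6-3.** After the pre-medication exemption in the corticosteroid row, add: *or short-term acute treatment of an infusion reaction as per Section 6.6.2.* State that any longer course above 10 mg/day stays under case-by-case review. The documents give no basis for a number of days, so the clinical team should set the limit.

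The cost is one bullet and one qualified phrase. No new data are needed and the analysis does not change. If blacked-out text in 6.2.2 already contains the exemption, only the first change is needed.
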